**Statistical Methods**
*General Considerations*

Descriptive summary statistics will be provided for demographics, disposition, and IMR-687 exposure. The number and percentage of subjects who discontinue from the study, along with reasons for discontinuations will be tabulated.

Continuous data will be summarized using descriptive statistics (number of subjects, mean, SD, median, Q1, Q3, minimum, and maximum) and, where appropriate, coefficient of variation (%CV) and graphic representation. Categorical data will be summarized by sample size and proportions. Data will be summarized by population (TDT, NTDT) and dose cohort at each timepoint as appropriate. Graphs of actual values and changes over time may also be created as appropriate.

Interim analyses will be conducted at each of the following milestones:

- 30 subjects in the TDT population have completed 24 weeks of treatment
- 30 subjects in the NTDT population have completed 24 weeks of treatment
- 60 subjects in the TDT population have completed 24 weeks of treatment
- 60 subjects in the NTDT population have completed 24 weeks of treatment

*Analysis Sets*

Note that each of the following populations are defined for TDT and NTDT populations separately. Combined TDT and NTDT populations may also be used as appropriate.

The safety analysis set will include all subjects who have received any amount of study drug and from whom informed consent has been obtained and will be used to summarize all safety and tolerability data. In safety summaries, subjects will be analyzed according to the actual treatment they received.

The per protocol set will include all subjects in the safety population who have provided sufficient data without major protocol deviations or events that would be expected to affect the analysis. The per protocol set will be identified based on blinded data prior to unblinding the final analysis dataset.

The per protocol set will be used to generate PD and clinical outcomes data.

The PK analysis set will be defined as a subset of the safety analysis set that includes all subjects who are enrolled in the study, have received at least 1 dose of IMR-687, and have sufficient IMR-687 concentration data; this set will be used in the PK analyses.

*Safety Analyses*

Descriptive statistics will be used to summarize all safety endpoints, by population and treatment

group as appropriate. Data summaries will be displayed for incidence of AEs, clinical laboratory variables, vital signs, and ECG parameters. Safety data summaries will use the safety analysis set. All AEs will be coded using MedDRA. Data will be summarized using preferred term and primary system organ class. AE summaries will include AEs leading to study discontinuation and severity and frequency of AEs and SAEs. All safety data will be summarized in by-subject listings.

*Preliminary Efficacy Analyses*

Population 1 (TDT)

Hematological improvement will be evaluated using a Cochran-Mantel-Haenzel (CMH) test to compare the proportion of subjects who achieved improvement between the placebo group to each of the 2 active treatment arms (IMR-687 lower dose and IMR-687 higher dose). Hematological improvement is defined as a  $\geq 20\%$  reduction in pRBC units transfused measured over 12 weeks (from Week 12 to Week 24 and from Week 24 to Week 36) as compared to the 12-week period prior to the Baseline (Day 1) visit. The safety and per protocol populations will be used, and no multiple comparisons adjustment will be made.

The mean number of transfusion events from baseline to Week 36 will be summarized by treatment group. Comparisons between placebo and each of the 2 active treatment arms (IMR-687 lower dose and IMR-687 higher dose) will be made using a t-test.

The mean change from baseline to Week 36 for ICT mean daily dose and serum ferritin will be analyzed using an analysis of covariance (ANCOVA) model with baseline value as a covariate and treatment as a factor.

Population 2 (NTDT)

The baseline value of Hb will be defined as the mean of non-missing Hb values from Screening (7 to 28 days prior to randomization) and randomization (Day 1) measurements. The baseline value of HbF will be defined in an analogous manner. The proportion of subjects with increase from baseline of  $\geq 1.0$  g/dL in mean Hb values (at Weeks 12 to 24 and Weeks 24 to 36) will be evaluated using a Cochran-Mantel-Haenzel (CMH) test to compare the proportion of subjects who achieved improvement between the placebo group and each of the 2 active treatment arms (IMR-687 lower dose and IMR-687 higher dose).

The average Hb concentrations in the absence of transfusions over a continuous 12-week interval (from Week 12 to Week 24 and from Week 24 to Week 36) as well as the change from baseline will be summarized by treatment group and timepoint. The change from baseline in average Hb at Weeks 12 to 24 and Weeks 24 to 36 will be compared between the placebo group and each of the 2 active treatment arms (IMR-687 lower dose and IMR-687 higher dose) using a mixed model for repeated measures (MMRM) with fixed effects for treatment group and timepoint and a random subject effect. The safety and per protocol populations will be used, and no multiple comparisons adjustment will be made. Mean change in HbF concentrations from baseline to Week 24 and to Week 36 will be analyzed in the same manner.

The number and proportion of subjects with HbF response of  $\geq 3\%$  using the mean values at Weeks 12 to 24 and Weeks 24 to 36 will be summarized by timeframe and treatment group. Comparisons of each of the 2 active treatment arms (IMR-687 lower dose and IMR-687 higher dose) to placebo will be made using a CMH test.

The mean change from baseline to Week 36 for ICT mean daily dose and serum ferritin will be analyzed using an ANCOVA model with baseline value as a covariate and treatment as a factor.

*Pharmacokinetic Analyses*

Summary statistics for trough plasma concentration ( $C_{trough}$ ) data will be provided. Accumulation may be assessed.

PK data from this study will also be used to explore any relationship between IMR-687 exposure and

clinical response, PD endpoints, or AEs, as data permit. These data will be analyzed together with PK data from other clinical studies for a population PK analysis, as appropriate.

#### *Analyses of Exploratory Endpoints*

Exploratory PD and clinical outcomes data for each timepoint will be listed by subject and summarized by treatment group separately for Population 1 (TDT) and Population 2 (NTDT) as appropriate. Correlations between PK and the exploratory endpoints may be assessed. Descriptive statistics will be computed as appropriate.

Summary statistics for QoL scores from the prespecified domains will be calculated at each administration timepoint. Summary statistics will also be calculated for change from baseline in each score at each administration timepoint.

Exploratory PD outcomes will be based on the PD analysis set, and QoL outcomes will be based on the safety and per protocol sets.

#### *Sample Size Calculations*

Both populations will have primary objectives of safety, and the sample sizes are not based on statistical assumptions.

#### Population 1 (TDT)

For the secondary efficacy endpoint of percentage of subjects with hematologic improvement (reduction in transfusion burden), 16 subjects in each treatment arm provide 80% power to detect a difference of 10% of subjects improving in the placebo arm versus 50% of subjects improving in either of the active treatment arms, using an alpha level of 0.05. No multiple comparisons adjustments will be made as these are secondary analyses.

#### Population 2 (NTDT)

For the secondary efficacy endpoint of proportion of subjects with increase from baseline of  $\geq 1.0$  g/dL in mean Hb values at Weeks 12 to 24 and Weeks 24 to 36, 17 subjects in each treatment arm provide >90% power to detect a difference of 10% of subjects improving in the placebo arm versus 50% of subjects improving in either of the active treatment arms, using an alpha level of 0.05. No multiple comparisons adjustments will be made as these are secondary analyses.

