#### **13.4.2. Population 2: Non-Transfusion Dependent $\beta$ -Thalassemia**

The baseline value of Hb will be defined as the mean of non-missing Hb values from Screening (7 to 28 days prior to randomization) and randomization (Day 1) measurements. The baseline value of HbF will be defined in an analogous manner.

The proportion of subjects with increase from baseline of  $\geq 1.0$  g/dL in mean Hb values (at Weeks 12 to 24 and Weeks 24 to 36) will be evaluated using a Cochran-Mantel-Haenzel (CMH) test to compare the proportion of subjects who achieved improvement between the placebo group and each of the 2 active treatment arms (IMR-687 lower dose and IMR-687 higher dose).

The average Hb concentrations in the absence of transfusions over a continuous 12-week interval (from Week 12 to Week 24 and from Week 24 to Week 36) as well as the change from baseline will be summarized by treatment group and timepoint. The change from baseline in average Hb at Weeks 12 to 24 and Weeks 24 to 36 will be compared between the placebo group and each of the 2 active treatment arms (IMR-687 lower dose and IMR-687 higher dose) using a mixed model for repeated measures (MMRM) with fixed effects for treatment group and timepoint and a random subject effect. The safety and per protocol populations will be used, and no multiple comparisons adjustment will be made. Mean change in HbF concentrations from baseline to Week 24 and to Week 36 will be analyzed in the same manner.

The number and proportion of subjects with HbF response of  $\geq 3\%$  using the mean values at Weeks 12 to 24 and Weeks 24 to 36 will be summarized by timeframe and treatment group.

Comparisons of each of the 2 active treatment arms (IMR-687 lower dose and IMR-687 higher dose) to placebo will be made using a CMH test.

The mean change from baseline to Week 36 for ICT mean daily dose and serum ferritin will be analyzed using an ANCOVA model with baseline value as a covariate and treatment as a factor.

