#### **13.7.1. Population 1: Transfusion Dependent $\beta$ -Thalassemia**

For the secondary efficacy endpoint of percentage of subjects with hematologic improvement (reduction in transfusion burden), 16 subjects in each treatment arm provide 82% power to detect a difference of 10% of subjects improving in the placebo arm versus 50% of subjects improving in either of the active treatment arms, using an alpha level of 0.1. No multiple comparisons adjustments will be made as these are secondary analyses.

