#### **13.7.2. Population 2: Non-transfusion Dependent $\beta$ -Thalassemia**

For the secondary efficacy endpoints of proportion of subjects with increase from baseline of  $\geq 1.0$  g/dL in mean Hb values at Weeks 12 to 24 or Weeks 24 to 36, 17 subjects in each treatment arm provide 84% power to detect a difference of 10% of subjects improving in the placebo arm versus 50% of subjects improving in either of the active treatment arms, using an alpha level of 0.1. No multiple comparisons adjustments will be made as these are secondary analyses.

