8.1.2 Population 2: Non-transfusion-dependent β-thalassemia

For the secondary efficacy endpoints of proportion of subjects with increase from Baseline of ≥ 1.0 g/dL in mean Hb values at Weeks 12 to 24 or Weeks 24 to 36, 30 subjects in an active arm and 15 subjects in the placebo arm will provide approximately 67% power to detect a difference of 10% of subjects improving in the placebo arm versus 50% of subjects improving in an active treatment arm, using a two-sided alpha level of 0.05. No multiple comparisons adjustments will be made as these are secondary analyses.

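### The synopsis claims more than 90% power for 17 NTDT subjects per arm at alpha 0.05; the inputs give about 75% two-sided and at most 88% one-sided, and Section 13.7 uses a different alpha

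*Protocol*

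**What the plan says.** The protocol gives the same power calculation twice, in the synopsis and in Section 13.7, with different alphas and results.

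- **Synopsis, NTDT:** "17 subjects in each treatment arm provide >90% power to detect a difference of 10% of subjects improving in the placebo arm versus 50" per cent on active treatment, "using an alpha level of 0.05".
- **Synopsis, TDT:** "16 subjects in each treatment arm provide 80% power to detect a difference of 10% of subjects improving in the placebo arm versus 50" per cent on active treatment, also at alpha 0.05.
- **Section 13.7.2, NTDT:** "17 subjects in each treatment arm provide 84% power" for the same rates, "using an alpha level of 0.1".
- **Section 13.7.1, TDT:** "16 subjects in each treatment arm provide 82% power" for the same rates, also at alpha 0.1.

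Neither place says whether alpha is one- or two-sided, and both rule out a multiplicity adjustment. Under Section 13.4.2 the NTDT responder proportion "will be evaluated using a Cochran-Mantel-Haenzel (CMH) test", each active arm against placebo.

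SAP 8.1.2 has a separate NTDT calculation with 30 active and 15 placebo subjects, "using a two-sided alpha level of 0.05", giving about 67% power. Both documents say that the sample sizes do not rest on statistical assumptions.

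**The concern.** Three things do not fit together.

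1. A power above 90% looks too high for 17 per arm with 10% against 50% at alpha 0.05.
2. Within the synopsis, the same rates and alpha give 80% for 16 per arm and more than 90% for 17 per arm. One subject per arm cannot account for that gap.
3. The synopsis and Section 13.7 use the same numbers per arm and the same rates, but alpha 0.05 in one and 0.1 in the other.

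A reader of the synopsis is told that the chance of missing a 50% against 10% effect is below 10%. If the true figure is about 25%, a null result would be over-interpreted. Sections 13.1 to 13.6 give no other significance level, so these two conflicting alphas are the only ones in the protocol.

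**Working it through.** **Inputs.** Placebo rate p0 = 0.10 and active rate p1 = 0.50 (synopsis and 13.7); n = 17 per arm (NTDT) and 16 per arm (TDT); alpha 0.05 (synopsis) or 0.1 (13.7); CMH test (13.4.2). No dropout allowance is stated, so none is used.

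**Pooled normal formula.** With p̄ = (0.10 + 0.50)/2 = 0.30,

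power = Φ{ [ (p1 − p0)√n − z√(2p̄(1 − p̄)) ] / √(p0(1 − p0) + p1(1 − p1)) }.

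Here √(2 × 0.30 × 0.70) = √0.42 = 0.6481 and √(0.09 + 0.25) = √0.34 = 0.5831.

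**Step 1: reproduce Section 13.7 (two-sided 0.1, z = 1.645).**

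- n = 17: 0.4√17 = 1.6492; (1.6492 − 1.645 × 0.6481)/0.5831 = 1.000; power 84.1%. Stated 84%.
- n = 16: 0.4√16 = 1.6; (1.6 − 1.0660)/0.5831 = 0.916; power 82.0%. Stated 82%.

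Both figures in 13.7 are right if alpha 0.1 is two-sided.

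**Step 2: the synopsis at two-sided 0.05 (z = 1.960).**

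- n = 17: (1.6492 − 1.960 × 0.6481)/0.5831 = 0.650; power 74.2%. Stated more than 90%.
- n = 16: (1.6 − 1.2702)/0.5831 = 0.566; power 71.4%. Stated 80%.

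**Step 3: the synopsis at one-sided 0.05.** The critical value is again 1.645, so the results are those of Step 1: 84.1% (NTDT) and 82.0% (TDT). The TDT figure of 80% is compatible with this reading. The NTDT figure is not.

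**Step 4: other methods, 17 per arm, alpha 0.05.** The CMH, Wald and Fisher values come from exact binomial enumeration. The unpooled formula is Φ{ 0.4√n/0.5831 − z }.

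| Method | Two-sided | One-sided |
|---|---|---|
| Pooled normal | 74.2% | 84.1% |
| CMH (planned test) | 75.0% | 85.0% |
| Unpooled normal | 80.7% | 88.2% |
| Continuity-corrected normal | 59.3% | 72.1% |
| Arcsine | 77.1% | 85.5% |
| Wald | 79.2% | 87.7% |
| Fisher | 62.6% | 74.7% |

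The highest value is 88.2%: 1.6492/0.5831 − 1.645 = 1.184. The same formula gives 86.4% for the TDT case stated as 80%, so it does not explain both synopsis figures.

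**Step 5: gain from one more subject per arm (16 to 17), two-sided 0.05.** Pooled: 74.2 − 71.4 = 2.8 points. CMH: 75.0 − 71.3 = 3.7 points. The largest gain by any method tried, one- or two-sided, is 4.9 points (continuity-corrected CMH). The synopsis implies more than 10.

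**Step 6: what more than 90% would need.** At two-sided 0.05, power first exceeds 90% at 25 per arm (CMH) or 26 (pooled). The most favourable one-sided formula needs 19. With 17 per arm, 90% power at two-sided 0.05 needs an active rate of about 60%.

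**The case against.** The best defence lies in the wording: the synopsis speaks of 50% improving in either of the active arms. Read as the chance that at least one of two active arms, both at 50% and sharing a placebo group, beats placebo, power with 17 per arm does pass 90% in some variants: CMH 95.0% one-sided and Wald 90.7% two-sided, though CMH two-sided is only 88.7%. Pooling both active arms (34 against 17) gives CMH 86.4% two-sided and 93.1% one-sided. The claim that the figure is unattainable therefore applies to the comparison of one active arm with placebo.

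This reading does not rescue the synopsis. Section 13.7.2 uses the same wording, and its 84% is reproduced by a single pairwise comparison. Under the at-least-one reading, the TDT case stated as 80% would come out between 86% and 94%. A one-sided alpha of 0.1 gives 92.0% for NTDT, but the synopsis states 0.05, and TDT would then be about 91%.

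Other points on that side carry weight. One-sided 0.05 and two-sided 0.1 share a critical value, so the clash of alphas may be partly a missing label. The protocol sets no success rule for these unadjusted secondary comparisons, and SAP 13.0 fixes two-sided p-values and 95% confidence intervals. The uncertainty over a two-sided p between 0.05 and 0.10 is therefore confined to the protocol text.

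**Conclusion.** The concern holds, as a minor one. The NTDT power in the synopsis is wrong as written. At two-sided 0.05 it is about 75% for the planned test, so the chance of missing a 50% against 10% effect is about 25%, not below 10%. At one-sided 0.05 it is 84% to 85%, and no pairwise method tried exceeds 88%. The two statements of alpha in the protocol also need reconciling.

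The TDT figure of 80% is not wrong in itself: it fits one-sided 0.05 (82%) but not two-sided 0.05 (71%). The 82% and 84% in Section 13.7 are correct at two-sided 0.1, and the SAP figures are not disputed.

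The result assumes one active arm against placebo, 17 evaluable subjects in each, and the stated rates. The impact is limited because safety is the primary objective, the sample size was not derived from power, and the SAP gives its own calculation.

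**What to change.** State one alpha, with its sidedness and the method used, in both the synopsis and Section 13.7, and delete the claim of more than 90%. There are two coherent options:

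- **Two-sided 0.05 (preferred, because it matches the SAP's alpha).** Give about 75% for NTDT (17 per arm) and about 71% for TDT (16 per arm), for the CMH test, in both places. These will still differ from the SAP figures, which use other arm sizes (30 against 15 and 30 against 20) and are reproduced by a continuity-corrected formula. The method should therefore be named.
- **Two-sided 0.1.** Copy the 84% and 82% from Section 13.7 into the synopsis with that alpha, and add the sidedness to 13.7.

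The cost is a text correction and a less favourable stated power. No subjects are added, no test changes, and the SAP is untouched.

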### 3. LIST OF ABBREVIATIONS

Abbreviation	Definition
%CV	coefficient of variation
AE	adverse event
ALT	alanine aminotransferase
AST	aspartate aminotransferase
AUC	area under the concentration-time curve
AUC 0-24	AUC from time 0 to 24 hours
BCRP	breast cancer resistance protein
CFR	Code of Federal Regulations
cGMP	cyclic guanosine monophosphate
C 24	concentration at 24 hours after study drug administration
C max	maximum plasma concentration
CMH	Cochran-Mantel-Haenzel
CNS	central nervous system
COVID-19	coronavirus disease 2019
CRO	contract research organization
CSR	clinical study report
C trough	trough plasma concentration
CYP	cytochrome P450
DMC	Data Monitoring Committee
DOAC	direct-acting oral anti-coagulant
ECG	electrocardiogram
eCRF	electronic case report form
EOT	end of treatment
FE	food effect
GCP	Good Clinical Practice
GI	gastrointestinal
GLP	Good Laboratory Practice
Hb	hemoglobin
HbE	hemoglobin E (abnormal variant)
HbF	fetal hemoglobin
HbS	hemoglobin S (abnormal variant)

Abbreviation	Definition
HED	human equivalent dose
HIV	human immunodeficiency virus
hsCRP	highly sensitive C-reactive protein
IB	Investigator's Brochure
IC 50	half-maximal inhibitory concentration
IC 90	concentration at which inhibition is 90%
ICAM-1	intercellular adhesion molecule 1
ICF	informed consent form
ICH	International Council for Harmonisation
ICT	iron chelation therapy
IEC	Independent Ethics Committee
IRB	Institutional Review Board
IWRS	interactive web response system
LDH	lactate dehydrogenase
MAD	multiple ascending dose
NCI CTCAE	National Cancer Institute Common Terminology for Adverse Events
NOAEL	No observed adverse effect level
NT-proBNP	N-terminal pro B-type natriuretic peptide
NTDT	non-transfusion-dependent ( $\beta$ )-thalassemia
NTDT-PRO	Non-transfusion Dependent $\beta$ -thalassemia Patient Reported Outcome
OECD	Organization for Economic Cooperation and Development
PD	pharmacodynamic(s)
PDE	phosphodiesterase
P-gp	P-glycoprotein
PK	pharmacokinetic(s)
pRBC	packed red blood cells
Q1	first quartile
Q3	third quartile
qd	once daily
QoL	quality of life
QTcF	corrected QT interval using Fridericia's formula

Abbreviation	Definition
RBC	red blood cell
SAD	single ascending dose
SAE	serious adverse event
SCD	sickle cell disease
SD	standard deviation
SF-36	Short Form (36) Health Survey
SUSAR	suspected unexpected serious adverse reaction
$t_{1/2}$	half-life
$t_{max}$	time to maximum plasma concentration
TDT	transfusion-dependent ( $\beta$ )-thalassemia
TEAE	treatment-emergent adverse event
TIBC	total iron binding capacity
TranQoL	Transfusion-dependent Quality of Life Questionnaire
ULN	upper limit of normal
VCAM-1	vascular cell adhesion molecule 1

## 4. INTRODUCTION

### 4.1. Overview of Disease Pathogenesis

The sponsor is developing IMR-687 for the treatment of adult subjects with  $\beta$ -thalassemia and sickle cell disease (SCD).

With an incidence of symptomatic individuals estimated at 1 in 100,000 worldwide ([Galenello 2010](#)),  $\beta$ -thalassemia is a rare inherited blood disorder characterized by the reduced or absent synthesis of the  $\beta$  chain of hemoglobin (Hb) and is caused by mutations in the hemoglobin beta (*HBB*) gene. The most common manifestations of  $\beta$ -thalassemia include reduced Hb in red blood cells (RBCs), decreased RBC production, and anemia ([Galenello 2010](#)). Clinically significant  $\beta$ -thalassemia is typically classified by the need for blood transfusions: non-transfusion-dependent  $\beta$ -thalassemia (NTDT) or transfusion-dependent  $\beta$ -thalassemia (TDT).

### 4.2. Overview of IMR-687 Development

#### 4.2.1. IMR-687

IMR-687 (6-[(3S,4S)-4-methyl-1-(pyrimidin-2-ylmethyl)pyrrolidin-3-yl]-3-tetrahydropyran-4-yl-7H-imidazo[1,5-a]pyrazin-8-one) is a potent, specific, and highly selective small molecule inhibitor of phosphodiesterase (PDE) 9; PDE9 mediates cellular signaling pathways by degrading cyclic guanosine monophosphate (cGMP) to its inactive or monophosphate form.

By inhibiting PDE9, IMR-687 is intended to increase cGMP levels and in doing so, stimulate the production of fetal hemoglobin (HbF), which reduces the cellular concentration of abnormal Hb (HbS) within RBCs and its associated sequelae. The importance of increasing HbF in treating SCD is evidenced by results from large studies like the Cooperative Study of Sickle Cell Disease in the US and studies in a variety of patient cohorts outside of the US showing that HbF is among the most important modifiers of this disease ([Platt 1991](#); [Platt 1994](#); [Alsultan 2013](#)), as well as data showing that modifiers of HbF improve other hematological parameters of SCD ([Akinsheye 2011](#); [Alsultan 2013](#); [Barbosa 2013](#); [Sheehan 2013](#)).

PDE9 is highly expressed in hematopoietic cells and is also widely distributed in the brain ([Fisher 1998](#); [Matsumoto 2003](#); [Nagasaki 2012](#)), with the highest expression measured in cerebellar Purkinje cells of rodents ([van Staveren 2002](#)). A potential advantage of IMR-687 for the  $\beta$ -thalassemia indication is that it does not readily distribute to the brain and, therefore, is less likely to result in the central nervous system (CNS) effects observed with other, brain-penetrating PDE9 inhibitors ([Schwam 2014](#); [Hutson 2011](#); [Van der Staay 2008](#)). Moreover, due to its specificity for PDE9, and the absence of evidence of genotoxicity and hepatotoxicity in Good Laboratory Practice (GLP) toxicology studies, IMR-687 could contribute to a meaningful improvement in the standard of care for patients.

